4.7. Sample size

We plan to randomise 710 women, 355 participants in each group. 670 women will need to be evaluated to detect a Minimally Important Difference (MID) of 10% reduction in the rate of failure to spontaneously pass the gestational sac within 7 days (i.e. from 25% to 15%), assuming 90% power and a type I error rate of 5%. However, assuming and adjusting for a worst case

scenario of 5% attrition, the total number of participants required will be 710. The 25% [95% CI: 23% to 27%] control group estimate is taken from our systematic review (unpublished data) and the 10% MID was the most popular selection from our health professional survey (41% of those surveyed). The estimate of the control group rate will be monitored throughout the recruitment period by the independent DMC to ascertain if any deviations from this assumption will impact on the sample size calculation.

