9.4. Data manipulations

The Trial Statistician will derive all responses from the raw data recorded in the database as follows:

Outcome measures

- **Failure to spontaneously pass the gestational sac within 7 days after randomisation**

Reported on PART E (treatment allocation) on the Randomisation Form and Section C (ultrasound scan) and Section E (surgical intervention) on the Outcomes Form by answering the following questions:

- a) Date of randomisation?
- b) Did the woman undergo scan(s) post-randomisation?
- c) If yes, was the sac passed?
- d) When was the date of scan?
- e) Did the woman require surgical intervention to resolve their miscarriage?
- f) When was the date of surgery?

The date of randomisation and date of scan will be used to calculate the number of days at which the scan was performed after randomisation. If the sac was passed as confirmed by an ultrasound scan, and it was passed within 7 days since randomisation and no surgical intervention was used to resolve the miscarriage before day 7 since randomisation, then the primary outcome will be coded as NO (i.e. not failed). If surgery for removing the sac was carried out within 7 days since randomisation, or the sac was not yet passed following the last scan which was performed at day 6-7 or beyond since randomisation then the primary outcome will be coded as YES (failed). If a woman did not undergo any scan after

randomisation and there was no surgery performed before day 7 since randomisation, or the last scan was undertaken within 5 days after randomisation and the sac was still present the primary outcome will be coded as MISSING, unless cases where the BERC unanimously decide that there is sufficient information available to confirm whether or not the primary outcome has been achieved and whether the sac was passed or not spontaneously by day 7 post-randomisation. The following questions from the Primary Outcome Review Form will be used to determine this:-

- A. Does the Committee unanimously agree that there is sufficient information available to confirm the primary outcome has been achieved?
- B. Does the Committee unanimously agree whether the sac was passed or not spontaneously by day 7 post-randomisation?
- C. Was the sac passed spontaneously by day 7 post-randomisation?
- D. Does the Committee unanimously agree on the date sac passed?
- E. Date sac passed

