If A, B, C and D are all yes and E is before the date of surgery if surgery was required, then the primary outcome is NO (not failed).

If A and B are Yes and C is No, then the primary outcome is YES (failed).

If either A or B are No then C is not answered and the primary outcome remains MISSING.

- **Surgical intervention to resolve the miscarriage (collected up to discharge from EPU care)**

Reported on Section E (Surgical intervention) on the Outcomes form by answering the question "Did the woman require surgical intervention to resolve their miscarriage?" where the date of surgery is on or before the EPU discharge date.

- **Surgical intervention to resolve the miscarriage up to and including day 7 post-randomisation**

Reported on Section E (Surgical intervention) on the Outcomes form by answering the question "Did the woman require surgical intervention to resolve their miscarriage?" where the date of surgery is ≤ 7 days after the randomisation date.

- **Surgical intervention to resolve the miscarriage after day 7 post-randomisation to discharge from EPU care**

Reported on Section E (Surgical intervention) on the Outcomes form by answering the question "Did the woman require surgical intervention to resolve their miscarriage?" where the date of surgery is >7 days after the randomisation date.

- **Need for further doses of misoprostol up to day 7 post-randomisation**

Reported on Section B (misoprostol administration) on the Outcomes Form by answering the question "Was misoprostol taken by the woman?" and if yes, "Date taken". Any further doses of misoprostol within 7 days since randomisation will be identified by calculating the time difference:

Date of misoprostol taken - Date of randomisation.

At least one of the time differences calculated above should fall within the range of 2 to 6 days inclusive and should not be the first dose to warrant a YES to the outcome measure.

- **Need for further doses of misoprostol up to discharge from EPU care**

Reported on Section B (misoprostol administration) on the Outcomes Form by answering the question "Was misoprostol taken by the woman?" and if yes, "Date taken" Any further doses of misoprostol throughout the trial will be identified by calculating the time difference:

Date of misoprostol taken - Date of randomisation.

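### SAP 9.4 leaves some women with two primary-outcome codes or none: surgery after sac passage, the day-7 limit and the committee's date question are handled inconsistently

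*SAP*

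**What the plan says.** SAP 9.4 derives failure to pass the sac spontaneously within 7 days by two routes.

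**Scan route.** Success (NO) needs a scan showing passage within 7 days and "no surgical intervention was used to resolve the miscarriage before day 7 since randomisation, then the primary outcome will be coded as NO". Failure (YES) follows "If surgery for removing the sac was carried out within 7 days since randomisation", or if the sac was still present at a last scan on day 6-7 or later. The outcome is MISSING, pending BERC review, in two branches: no scan, provided "there was no surgery performed before day 7 since randomisation"; or a last scan within 5 days with the sac still present. The second branch has no surgery condition.

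**BERC route.** The committee answers five questions: A, enough information; B, agreement on whether the sac passed spontaneously by day 7; C, whether it did; D, agreement on the date; E, the date. Success is coded "If A, B, C and D are all yes and E is before the date of surgery if surgery was required". Failure is coded more simply: "If A and B are Yes and C is No, then the primary outcome is YES (failed". A No to A or B leaves the outcome MISSING.

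**Remit.** Section 4.3 sends to the BERC women with no scan within 7 days, or with a scan whose result on passage was not recorded. It says nothing about surgery.

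**The concern.** The two routes treat surgery after spontaneous passage differently. The scan route bars success for surgery before day 7 regardless of order; the BERC route looks only at whether passage came first. The same clinical course can therefore get a different code according to how it was documented.

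The day-7 limit also differs between rules. Review is scheduled for day 6-7 (Appendix C), so surgery on day 7 is plausible. Finally, the BERC success rule needs a unanimous date although the endpoint needs only passage by day 7.

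Where two rules apply, or none does, someone must decide at analysis how to code the primary outcome, which is what a SAP exists to prevent. The sensitivity analysis in 9.10 that removes BERC-determined women would, for the women concerned, change the surgery rule together with the source of information.

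**Working it through.** **1. The rules applied literally.** The sac is taken to have passed on day 3 unless stated otherwise.

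| Course | Code under the 9.4 scan, surgery and MISSING rules | Code under the BERC rules |
|---|---|---|
| Clear scan day 3, surgery day 5 or 6 | Never NO. YES if the surgery counts as removing the sac, otherwise no code | Not sent |
| Last scan day 2, sac present; surgery day 5 or 6 | MISSING (to BERC), and YES if counted as sac removal | NO |
| No scan, surgery day 5 or 6 | Not MISSING. YES if counted as sac removal, otherwise no code | In the 4.3 remit; if reviewed, NO |
| No scan, surgery day 7 | MISSING (to BERC), and YES if day 7 is within 7 days and the surgery counts as sac removal | NO |
| Clear scan day 3, surgery day 7 | NO, and YES only on the same two readings | Not sent |
| Surgery day 8 or 10 | NO with a clear scan; MISSING (to BERC) with no scan | NO |
| Reviewed; A, B, C Yes and D No | MISSING pending review | No code |
| Reviewed; A to D Yes, E equal to the surgery date | Depends on branch | No code |
| Only scan on day 9, sac passed, no surgery | No code | In the 4.3 remit |

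For surgery after day 7 the routes agree. Before day 7 they cannot both give NO.

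**2. How women with surgery by day 7 reach the BERC.** There are three ways: the early-scan MISSING branch, surgery on day 7 itself, and the remit in 4.3. That remit differs from the MISSING set in both directions. It includes unscanned women with surgery before day 7, whom 9.4 leaves out. It omits women with a recorded early scan showing the sac, whom 9.4 puts in.

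**3. The 7-day window elsewhere in 9.4.** The early-surgery outcome counts surgery up to and including day 7. The further-misoprostol outcome turns its 7-day window into days 2 to 6. Both conventions are in use.

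**4. The date question.** The lead-in to the BERC rules lifts MISSING once the committee is unanimous that the information suffices and on whether the sac passed by day 7, which is A and B. The coding rule for success then adds D; the rule for failure does not. D = No can therefore remove only agreed successes.

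**5. Size.** The baseline comes from SAP 4.7: "i.e. from 25% to 15%), assuming 90% power and a type I error rate of 5" per cent. Two-sided, pooled variance, no continuity correction:

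n = [1.960√(2 × 0.20 × 0.80) + 1.282√(0.25 × 0.75 + 0.15 × 0.85)]² / 0.10² ≈ 334.2, so 335 per arm and 670 in all.

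This reproduces the plan: "670 women will need to be evaluated to detect a Minimally Important Difference (MID) of 10% reduction". With 5% attrition, 670/0.95 = 705.3, so 706 against the stated 710. The sample size is not in error. Power at 335 per arm is 90.1% and the planned risk ratio is 0.15/0.25 = 0.60.

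The SAP gives no rate for any affected group, so these are assumptions. Suppose 20% of successes are BERC-reviewed.

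- *Date gap.* If 10% of those have D = No, 0.20 × 0.10 = 2% of successes are lost. Control: 0.25/(0.25 + 0.75 × 0.98) = 25.4%. Treated: 0.15/(0.15 + 0.85 × 0.98) = 15.3%. The risk ratio is 0.601. If the whole loss fell in one arm, it would be 0.1526/0.25 = 0.610 or 0.15/0.2538 = 0.591.
- *Surgery after passage.* Suppose a share x of all women pass the sac and then have surgery by day 7, and 20% of these are reviewed. The route then decides the code for 0.20x of women. With x = 1%: 0.152/0.252 = 0.603. With x = 5%: 0.16/0.26 = 0.615, with power 89.0%.

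**The case against.** Several points on the other side stand.

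- A reader might infer that any unscanned woman with early surgery after passage is coded a success by the BERC. Section 9.4 does not support that: its no-scan MISSING branch excludes surgery before day 7. The conflict is confined to the three ways in described above.
- A reader might infer that day-7 surgery after a clear scan always meets both NO and YES. That depends on reading. The failure rule speaks of removing the sac, which a woman who has already passed it would not naturally meet, and on the misoprostol outcome's usage within 7 days ends at day 6. This does not rescue surgery before day 7, where NO remains barred. The derivation items ask only about surgery to resolve the miscarriage and its date. Appendix D7.1 also tabulates the reason for surgery, but its categories do not cleanly separate the sac from residual tissue.
- Counting all surgery by day 7 as failure is coherent with the primary objective, which speaks of resolution within 7 days. That is a legitimate definition. The defect is that only one route uses it.
- A reader might infer a material loss of power or clearly inflated failure rates. Such figures require assumed rates applied to every woman, whereas the date gap reaches only BERC-reviewed women. Nor does the 9.10 analysis compare a wholly different endpoint, since the surgery conflict concerns only women with surgery by day 7.

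**Conclusion.** The concern holds in this limited form: the rules of 9.4, followed as written, give some women two codes or none on the primary outcome. Three gaps are established: opposite treatment of surgery by day 7 after passage, for women who can reach the BERC; an unreconciled day-7 boundary, clearest for unscanned women with day-7 surgery; and no code when D is No or when E is not before surgery.

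The number of women is not given and is probably small. On the assumptions shown, the risk ratio stays between 0.591 and 0.615, so a changed conclusion is not demonstrated. The case for acting rests on the endpoint being undefined for these women and on the one-directional loss of agreed successes.

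**What to change.** Amend 4.3 and 9.4 before the statistician is unblinded:

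1. State one rule, for both routes, on whether surgery by day 7 after spontaneous passage is a failure. Coding by whether passage preceded surgery matches the endpoint's name; counting all such surgery as failure would fit the resolution objective. Either can be defended if it is applied to both routes.
2. Use one boundary, 7 days or fewer from randomisation, in the NO, YES and MISSING rules, as the early-surgery outcome already does.
3. Add a surgery condition to the early-scan MISSING branch, and make the BERC remit in 4.3 the same set as in 9.4, including women whose only scan is after day 7 and shows passage.
4. Code NO when A, B and C are Yes. Require D and E only if surgery took place on or before day 7, and state the code when E is not before surgery.

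The cost is SAP wording and derivation code. No new data are needed.

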4.1. Trial design

MifeMiso is a randomised, parallel group, double-blind, placebo-controlled multicentre study, with health economic and mixed-methods evaluation (see Appendix B for trial schema).

Potential participants will be recruited from Early Pregnancy Assessment Units (EPAUs) of participating centres.

Women diagnosed with missed miscarriage by pelvic ultrasound scan in the first 13+6 weeks of pregnancy that choose to have medical management of miscarriage will be randomised to mifepristone plus misoprostol (MifeMiso combination) or misoprostol alone.

It is anticipated that the trial will last for three years. Women will be followed up until final discharge which is usually after 21±2 days since randomisation. A semi-structured qualitative interview will be conducted on a subset of participants within 6 weeks of discharge.

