4.6. Randomisation

Randomisation will be performed on-line on a 1:1 ratio via a secure internet facility through a third party independent Integrated Trial Management System (MedSciNet Clinical Trial Framework). A "minimisation" procedure using a computer-based algorithm will be used to avoid chance imbalances in the following important variables:

- Maternal age (<30, \geq 30 years);
- Body mass index (<35, \geq 35 kg/m²);
- Previous parity (nulliparous, parous women);
- Gestational age (<70, \geq 70 days);
- Amount of bleeding (Pictorial Blood Assessment Chart score \leq 2, \geq 3);
- Randomising centre.

A 'random element' will be included in the minimisation algorithm, so that each woman has a probability (unspecified here) of being randomised to the opposite treatment that they would have otherwise received.

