9.1. Covariate adjustment

In the first instance, all estimates of treatment effects between groups for all outcomes will be adjusted for the minimisation variables as listed in Section 4.6, where maternal age, body mass index and gestational age will be treated as continuous fixed effects, parity and bleeding score as categorical fixed effects, and randomising centre will be included as a random effect.

If covariate adjustment is not possible (e.g. the model does not converge), centre will be dropped from the model in the first instance. If convergence of the model remains problematic, alternative models will be explored (e.g. Poisson regression). If this fails, unadjusted estimates will be produced, and it will be made clear in the final report why this occurred (e.g. not possible due to low event rate/lack of model convergence).

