9.2. Distributional assumptions and outlying responses

Distributional assumptions (e.g. normality of regression residuals for continuous outcomes) will be assessed visually (via histograms for any continuous data) prior to analysis; although in the first instance the proposed primary method of estimation stated in this analysis plan will be followed. If responses are considered to be particularly skewed and/or distributional assumptions violated and potentially affecting the analysis then this will be examined through sensitivity analysis consisting of transformations or bootstrapping techniques. In the case of skewed distributions of continuous responses, this will consist of transformation of responses prior to analysis (log transformation in the first instance, although others may be used if deemed appropriate). If extreme values are apparent and considered to be affecting the integrity of the analysis, a sensitivity analysis consisting of removing the outlying response(s) and repeating the analysis will be performed. Output from these analyses, if performed, will be described and presented alongside the primary analysis with the excluded values clearly labelled. See section 9.10 for further details regarding sensitivity analyses.

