At least one of the time differences calculated above should be greater than or equal to 2, should be taken on or before the date of discharge from EPU care, and should not be the first dose to warrant a YES to the outcome measure.

- **Overall patient satisfaction score (measured using CSQ-8 questionnaire and collected upon discharge from EPU care)**

The outcome will be defined using a validated eight item client satisfaction questionnaire (CSQ-8)⁹. The CSQ-8 is a widely used instrument for assessing client satisfaction with health and human services, and has been used in previous trials of treatment for miscarriage¹⁰. The CSQ-8 is a brief, standardized measure of client satisfaction that is comprised of eight items. Each item asks respondents to provide their opinion and conclusions about services they have received. Each question is scored out of four. The overall score is produced by summing all item responses, with total scores ranging from 8-32 points, with higher scores indicating higher levels of satisfaction.

- **Duration of bleeding reported by woman (days) (collected up to discharge from EPU care)**

Reported on Section F (clinical outcomes until discharge) on the Outcomes form by answering "Date woman reported that bleeding started" and "Date woman reported that bleeding stopped", where days of bleeding will be computed from:

Date woman reported that bleeding stopped - Date woman reported that bleeding started.

This outcome will be treated as continuous.

- **Diagnosis of infection associated with miscarriage requiring outpatient antibiotic treatment (collected up to discharge from EPU care)**

Reported on Section F (clinical outcomes until discharge) on the Outcomes form by answering YES consecutively to the following three questions:

- a) Was the woman diagnosed with an infection that was associated with miscarriage?
- b) Were they treated as an outpatient?
- c) Was the woman prescribed antibiotics for the infection?

A binary outcome will be defined based on whether or not the above three conditions were satisfied simultaneously. If any are missing then the outcome will be coded as MISSING.

- **Diagnosis of infection associated with miscarriage requiring inpatient antibiotic treatment (collected up to discharge from EPU care)**

Reported on Section F (clinical outcomes until discharge) on the Outcomes Form by answering YES consecutively to the following three questions:

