9.6. Analysis methods – secondary outcomes

Analyses for the binary secondary outcomes will be performed as per the primary outcome for the following outcome measures

- **Surgical intervention to resolve the miscarriage (collected up to discharge from EPU care)**
- **Surgical intervention to resolve the miscarriage up to and including day 7 post-randomisation**
- **Surgical intervention to resolve the miscarriage after day 7 post-randomisation to discharge from EPU care**
- **Need for further doses of misoprostol up to day 7 post-randomisation**
- **Need for further doses of misoprostol up to discharge from EPU care**
- **Diagnosis of infection associated with miscarriage requiring outpatient antibiotic treatment (collected up to discharge from EPU care)**
- **Diagnosis of infection associated with miscarriage requiring inpatient antibiotic treatment (collected up to discharge from EPU care)**
- **Negative pregnancy test result 21 days (\pm 2 days) after randomisation**
- **Blood transfusion required (collected up to discharge from EPU care)**
- **Side effects (AEs collected up to discharge from EPU care)**
- **Death (collected up to discharge from EPU care)**
- **Any serious complications (SAEs collected up to discharge from EPU care)**

95% confidence intervals (and p-values for the key secondary outcome and safety outcomes) from the associated models will be presented according to the strategy detailed in section 5.2. No sensitivity analyses for these secondary outcome measures will be performed.

A template for reporting these binary secondary outcomes is given in Appendix D7.1 and D9.1.

Linear regression modelling will be used to compare

- **Overall patient satisfaction score (measured using the CSQ-8 questionnaire and collected upon discharge from EPU care).**
- **Duration of bleeding reported by woman (days) (collected up to discharge from EPU care)**

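### Bleeding duration has no value for a woman without a stop date by discharge, so the longest bleeds can leave the analysis; its start date is also not anchored at randomisation

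*SAP*

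**What the plan says.** SAP section 9.4 defines the outcome as "Duration of bleeding reported by woman (days) (collected up to discharge from EPU care") and derives it as "Date woman reported that bleeding stopped - Date woman reported that bleeding started". It adds: "This outcome will be treated as continuous". No rule is given for a woman who has no stop date, and the randomisation date does not enter the formula.

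Section 9.6 gives the analysis: "Linear regression modelling will be used to compare" the arms on this outcome, reporting an adjusted mean difference, with Poisson regression and robust standard errors if the residuals are too skewed. No censoring or time-to-event method is named.

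On follow-up, section 4.1 says: "Women will be followed up until final discharge which is usually after 21±2 days since randomisation".

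On bleeding at entry, section 4.6 lists "Amount of bleeding (Pictorial Blood Assessment Chart score" as a minimisation factor, split at 2 or less against 3 or more. Section 9.1 carries it into the models: "parity and bleeding score as categorical fixed effects".

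The missing-data rules in section 9.3 concern the primary outcome, and section 9.10 limits sensitivity analyses to it. Under sections 5.1 and 5.2 bleeding duration is exploratory, with a 95% confidence interval and no p-value.

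**The concern.** A difference of two dates exists only when both dates exist. If bleeding continues at discharge there is no stop date to enter, so the woman has no outcome value. She is missing because her bleed is long. That is missingness on the outcome itself, and adjustment for the minimisation variables does not remove it. Duration of bleeding is named in the secondary objectives (section 3) and will be reported as an estimate with an interval, so readers will take the figure at face value.

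The second gap is the start of the clock. Minimising on amount of bleeding implies that some women may already be bleeding when randomised. Their reported start date can precede treatment, and days before treatment cannot respond to it. Elsewhere in section 9.4 the further-misoprostol outcomes and time to discharge are counted from randomisation; this outcome is not.

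**Working it through.** The SAP states no mean, SD, share bleeding at entry or share bleeding at discharge, so there is no figure to reproduce. The calculations below show direction and possible size only. Every distribution in them is an assumption.

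**1. Does anything in the SAP supply the missing value?** Section 9.4 gives missing-value rules for infection, pregnancy test and transfusion, but none for bleeding duration. Section 9.3 and the multiple imputation in section 9.10 are for the primary outcome. The transformation, bootstrap and outlier steps in section 9.2 act on values that exist. So nothing does.

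**2. Effect of losing women still bleeding.** Inputs:
- Gamma durations with the same shape k in both arms and mean m (scale m/k).
- A true difference of −2.0 days, treated minus control.
- A window of W = 19 days from bleeding start to discharge. This is assumed, for example a bleed starting on day 2 and discharge on day 21.

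With F(W; k) the gamma distribution function:
- share without a stop date = 1 − F(W; k)
- mean among women with a stop date = m × F(W; k+1) / F(W; k)
- mean if durations are cut at discharge = m × F(W; k+1) + W × [1 − F(W; k)]

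Worked case, k = 4, means 14 and 12:
- Control: 1 − 0.7901 = 21.0% lost; mean 14 × 0.6313 / 0.7901 = 11.19.
- Treated: 1 − 0.8762 = 12.4% lost; mean 12 × 0.7571 / 0.8762 = 10.37.
- Estimated difference 10.37 − 11.19 = −0.82 instead of −2.0.
- Cut at discharge: control 14 × 0.6313 + 19 × 0.2099 = 12.83; treated 12 × 0.7571 + 19 × 0.1238 = 11.44; difference −1.39.

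| Means, control / treated (control SD) | No stop date, control v treated | Difference, women with a stop date | Difference, cut at discharge |
|---|---|---|---|
| 12 / 10 (6) | 12.4% v 5.5% | −1.11 | −1.64 |
| 12 / 10 (8) | 16.8% v 9.9% | −0.79 | −1.39 |
| 14 / 12 (7) | 21.0% v 12.4% | −0.82 | −1.39 |
| 14 / 12 (8) | 22.7% v 14.6% | −0.71 | −1.28 |
| 16 / 14 (8) | 30.2% v 21.0% | −0.61 | −1.14 |

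The size depends heavily on W. In the 14 / 12 (7) case with W = 28, the losses are 4.2% v 1.7% and the difference is −1.50.

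**3. Is the bias always towards zero?** No. Take both arms with mean 12 and SD 6, so no true difference. Lose the longest 10% in one arm and the longest 5% in the other. The remaining means are 10.61 and 11.18, a spurious difference of −0.57 days.

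**4. Effect of days before randomisation.** Suppose a share p of women have exponential pre-randomisation bleeding with mean 5 days, distributed alike in both arms because it precedes randomisation.
- Mean difference: (10 + 5p) − (12 + 5p) = −2 for any p. There is no bias.
- Added variance: 2 × 25p − (5p)² = 50p − 25p². With a post-randomisation SD of 6 (variance 36), p = 0.2 gives 36 + 9 = 45 and p = 0.3 gives 36 + 12.75 = 48.75. The unadjusted standard error rises by √(45/36) − 1 = 12% and √(48.75/36) − 1 = 16%. Efficiency falls by 1 − 36/45 = 20% and 1 − 36/48.75 = 26%. Adjustment for bleeding score recovers part of this.
- Ratio of means, as a log-link Poisson fallback would give: 10/12 = 0.83 becomes (10 + 5p)/(12 + 5p), which is 0.84 at p = 0.1 and 0.86 at p = 0.5.

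**The case against.** The strongest reply is that the SAP nowhere says women still bleeding are excluded, and the Outcomes Form is not shown; it may have a convention for ongoing bleeding or for the start date. That is fair. Exclusion is an inference from a formula that cannot be evaluated without a stop date. It stands unless such a convention exists, and the SAP states none.

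The 19-day window is also open to challenge. Day 21 ± 2 is the discharge point for women with a negative pregnancy test (Appendix C). Others stay under follow-up, and some long bleeds will be observed. The loss may therefore be well below the table's figures, as the 28-day case shows.

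A reader might infer that pre-randomisation days dilute the treatment effect. On the planned mean-difference scale they do not; they cost precision. A reader might also infer that a same-day bleed scored 0 breaks the log transformation ("log transformation in the first instance"). Section 9.2 allows other transformations, and the Poisson fallback in section 9.6 accepts zeros. Whether both end days are counted is likewise immaterial: a constant added for every woman who bled cancels in their mean difference.

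Finally, censoring at discharge is not a clean remedy. Section 9.4 dates final discharge after a negative pregnancy test, which may be related to bleeding having ended. This stands and limits the fix.

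**Conclusion.** The concern holds in a limited form. As written, the derivation gives no value to a woman without a stop date by discharge, her absence depends on how long she bled, and no planned analysis covers it. In the assumed scenarios with a 19-day window, a true 2.0-day difference shrinks by about 45% to 70%. It would be wrong to conclude that the bias always runs towards no difference, since unequal loss can create one. The missing anchor at randomisation is a lesser matter of precision, and of slight dilution if a ratio is reported.

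All sizes rest on assumed means, SDs, prevalences and window; the SAP fixes none of them. The outcome is exploratory without a p-value, and the primary and key secondary conclusions are untouched. The point is minor to moderate, and worth correcting because the correction is cheap.

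**What to change.** Amend section 9.4, before unblinding, as follows.
- Count from the later of the reported start date and the randomisation date. Score women with no bleeding after randomisation as 0.
- Keep women still bleeding at discharge, censored there, in a restricted-mean or Kaplan–Meier analysis. Set the horizon no later than the follow-up common to nearly all women, for example day 19 (21 − 2, from section 4.1).
- If the linear model is kept as the main analysis, add at least a sensitivity analysis that sets the duration of these women to their discharge date. In the table this recovers part of the difference (−1.1 to −1.6 against −2.0), not all of it.
- Report the number of women without a stop date by arm in Appendix D7.2.

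The cost is SAP wording and one further analysis. The randomisation, start, stop and discharge dates are already collected, but it must be confirmed that a blank stop date means ongoing bleeding and not an unrecorded date. The downsides are that the effect becomes a restricted mean difference instead of a plain one, and that censoring at discharge may itself be informative, which the report should say.
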